7.3 Baseline Disease Evaluation

Summary of medical and psychiatric history will be presented for the randomized analysis set by treatment group and overall.

Binge eating days and number of binge eating episodes at baseline will be summarized for the randomized analysis set by treatment group and overall.

Descriptive statistics for efficacy scales at baseline will be provided for the randomized analysis set by treatment group and overall, including binge eating days per week, binge eating episodes per week, CGI-S score, Y-BOCS-BE total score and subscale scores for obsession and compulsion, PGI-S score, EDE-Q7 global score and subscale scores for dietary restraint, shape/weight overvaluation, and body dissatisfaction, SF-36v2 PCS and MCS scores, HAM-A total score, and MADRS total score.

7.4 Treatment Compliance

Based on the IMP panel of the eCRF, compliance of taking IMP is calculated by dividing the number of tablets taken by the total number of tablets the subjects are scheduled to take during the trial period. For lost-to-follow up subjects, last IMP end date record are used as the treatment end date. Compliance rate will be summarized for the randomized analysis set by treatment group in categories of < 80%, 80% to <90%, 90% to <100%, >100% etc.

7.5 Prior and Concomitant Medications

Number and proportion of subjects taking concomitant medications will be presented for randomized analysis set by treatment group and drug classification using the World Health Organization (WHO) drug dictionary for the following three intervals: prior to start of double-blind treatment period, during double-blind treatment period, and post study therapy.

7.6 Protocol Deviations

Major protocol deviations will be summarized for randomized analysis set by center and type of deviation for randomized subjects in addition to by treatment group and type of deviation. Listing of protocol deviation will be provided. In addition, protocol deviations due to COVID-19 will be summarized by center and type of deviation for randomized subjects. Listing of subjects with protocol deviations affected by the COVID-19 will also be provided.

8 Efficacy Analysis

8.1 Estimands

8.1.1 Primary Estimand

The primary clinical question of interest is: what is the treatment difference in binge eating days per week after 8 weeks of centanafadine treatment compared to placebo treatment in adult subjects with moderate to severe BED, where no subject would discontinue treatment due to any reason?

The primary estimand has the following attributes:

- Population: adult subjects with moderate to severe BED who meet the inclusion/exclusion criteria.
- Endpoint: change from baseline in binge eating days per week at Weeks 7-8.
- Intercurrent events: premature treatment discontinuation.
- Treatment condition: one of the randomized treatment groups of the following per protocol: high dose centanafadine 400 mg TDD, low dose centanafadine 200 mg TDD, or placebo.
- Population-level summary: difference in mean of endpoint between treatment conditions.
- Rationale for estimand: the hypothetical estimand is to evaluate the pharmacological effect if no withdrawals had occurred. It is justifiable since the focus is on the pharmacological effect of the drug additional to non-specific effects. Subjects who withdraw from a symptomatic IMP treatment either could have lost the treatment effect if the subjects had not taken any other symptomatic medication after withdrawal or could have the treatment effect masked if the subjects had taken other symptomatic medication after withdrawal. In those cases, any observations taken after subjects stop IMP will most likely not contribute to relevant information about the pharmacological effect of the drug. Therefore, the last collected efficacy assessment after premature trial discontinuation will be performed only once at the ET Visit.

8.1.2 Secondary and Other Estimands

The clinical question of interest for the key secondary estimand is: what is the treatment difference in CGI-S Score after 8 weeks of centanafadine treatment compared to placebo treatment in adult subjects with moderate to severe BED, where no subject would discontinue treatment due to any reason?

The key secondary estimand has similar attributes to the primary estimand except that key secondary endpoint is change from baseline in CGI-S score at Week 8. Other estimands have similar attributes to the primary and key secondary estimands.

8.2 Primary Efficacy Endpoint

The primary efficacy endpoint is the change from baseline in binge eating days per week at Week 7-8, having binge eating day defined as a day with at least one confirmed binge eating episode by principal investigator.

8.2.1 Primary Efficacy Analysis

The primary efficacy endpoint is the change from baseline in binge eating days per week at Weeks 7-8, having binge eating day defined as a day with at least one binge eating episode. The primary estimand defining the treatment effect of interest in the trial uses the hypothetical strategy specified in the draft ICH E9 (R1) Addendum⁸. In the hypothetical strategy, the event of withdrawing IMP is considered MAR, and the primary endpoint of the trial could be considered as a combination of the responses of ontreatment completers at Week 8 and the imputation of the endpoint to Week 8 following the trend in each treatment group using the MMRM method for subjects who withdraw IMP during the trial. All data collected during the trial treatment period will be used for statistical analysis.

[figure not shown]
The comparison between the centanafadine groups and the placebo group will be tested at a significance level of 0.05 (2-sided) in a fixed sequence testing of 1) high dose centanafadine versus placebo, and 2) low dose centanafadine versus placebo, in which Test 2) won't be performed unless Test 1) is statistically significant.

The primary efficacy analysis will be performed by fitting an MMRM analysis with an unstructured variance covariance structure, in which change from baseline in binge eating days per week at the scheduled visits will be the dependent variable. The model will include fixed effect terms for treatment, trial center, visit week, and an interaction term of treatment by visit week. The model will also include the interaction term of baseline values of binge eating days per week by visit week as covariates. The level of visit in the MMRM will include Week 1, Week 2, Week 3, Week 4, Week 6, and Week 8. The primary comparison between centanafadine groups and the placebo group at Week 7-8 will be estimated as the difference between least squares means utilizing the computing software SAS procedure PROC MIXED.

If there is a convergence problem with the unstructured variance covariance matrix of the MMRM model, the following structures other than unstructured will be used in order of 1) heterogeneous toeplitz, 2) heterogeneous autoregressive of order 1, and 3)

heterogeneous compound symmetry and the first (co)variance structure converging to the best fit will be used as the primary analysis. If a structured covariance has to be used, the "sandwich" estimator of the standard error of the fixed effects parameters will be used in order to deal with possible model misspecification of the covariance matrix.

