The primary efficacy analysis will be performed by fitting an MMRM analysis with an unstructured variance covariance structure, in which change from baseline in binge eating days per week at the scheduled visits will be the dependent variable based on the OC data set. The model will include fixed effect terms for treatment, trial center, visit week, and an interaction term of treatment by visit week. The model will also include the interaction term of baseline values of binge eating days per week by visit week as covariates. The level of visit in the MMRM will include Week 1, Week 2, Week 3, Week 4, Week 6, and Week 8. The primary comparison between centanafadine groups and the placebo group at Weeks 7-8 will be estimated as the difference between Least Squares means utilizing the computing software SAS procedure PROC MIXED. If there is a convergence problem with the unstructured variance covariance matrix of the MMRM model, the following structures other than unstructured will be used in order of 1) heterogeneous toeplitz, 2) heterogeneous autoregressive of order 1, and 3) heterogeneous compound symmetry and the first (co)variance structure converging to the best fit will be used as the primary analysis. If a structured covariance has to be used, the "sandwich" estimator of the standard error of the fixed effects parameters will be used in order to deal with possible model misspecification of the covariance matrix. Details of this analysis will be provided in the SAP.

Within MMRM analysis, baseline is defined as the last available measurement prior to the first dose of IMP in the double-blind treatment period and small centers will be pooled as needed. The linear model assumptions will also be checked. Details will be provided in the SAP.

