3.3 Trial Population

Subjects are 18 to 65 years of age (inclusive), with a primary diagnosis of BED of at least moderate severity, with a history of at least 2 binge eating days per week for 6 months prior to screening and at least 3 binge eating days in each week during the previous 14 days of a subject's screening period according to the subject's binge diary as reviewed at baseline, a rating of 4 or higher on the Clinical Global Impression - Severity (CGI-S) at screening and baseline, and a body mass index (BMI) of 18 to 45 kg/m², inclusive. Subjects with a lifetime history or current diagnosis of bulimia nervosa or anorexia nervosa are excluded.

Approximately 228 adult subjects with BED are anticipated to be screened with the expectation that approximately 126 eligible subjects are to be randomized (42 subjects per treatment arm). The randomization is stratified by trial site.

4 Sample Size

Assuming a treatment difference of 1.1 points with a standard deviation of 1.7 in the mean change from baseline in binge eating days per week at Weeks 7-8 in either centanafadine dose group (high dose centanafadine or low dose centanafadine) compared to the placebo group (effect size = 0.65), a sample size of 114 evaluable subjects (38 in each treatment arm) yield at least 80% power to detect the treatment effects at a 2-tailed significance level of 0.05. Approximately 126 subjects are randomized to ensure 114 evaluable subjects in the study. The power and sample size were obtained using the PASS 14 (2015) statistical computing software.

5 Statistical Analysis Datasets

The following datasets are defined for this trial:

- Randomized Analysis Set comprises all subjects who are randomized in the double-blind treatment period. Subjects are considered randomized subjects when they are assigned a treatment group at the baseline visit.
- Safety Analysis Set comprises those randomized subjects in the double-blind treatment period who receive at least 1 dose of double-blind IMP. Subjects will only be excluded from this population if there is documented evidence (ie, numbers of drug dispensed are equal to numbers of drug returned, or no IMP dispensed at all) that the subject did not take IMP. If a subject is dispensed IMP and is lost to follow-up, he/she is considered as exposure to IMP.

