8.2.3.2 Pooling Centers

Small centers will be defined as centers that do not have at least one subject with the evaluable primary efficacy endpoint) in each treatment arm. All small centers will be pooled to form "pseudo centers" for the purpose of analysis according to the following algorithm. Small centers will be ordered from the largest to the smallest based on the number of evaluable subjects (ie, subjects who have baseline and at least one post-baseline value for the primary endpoint). The process will start by pooling the largest of the small centers with the smallest of the small centers until a non-small center is formed. This process will be repeated using the centers left out of the previous pass. In case of

ties in center size, the center with the smallest center code will be selected. If any centers are left out at the end of this process, they will be pooled with the smallest pseudo centers, or if no pseudo centers exist, they will be pooled with the smallest non-small center.

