8.2.3.3 Data Processing Convention

The SAS code for the PROC MIXED procedure to carry out the above MMRM analysis with an unstructured variance-covariance structure is illustrated as follows:

PROC MIXED:

CLASS treatment center visit subjid;

MODEL change=treatment center visit treatment*visit baseline*visit / S CL DDFM=KENWARDROGER;

REPEATED visit /TYPE=UN SUBJECT=subjid R RCORR;

LSMEANS treatment*visit / PDIFF CL ALPHA=0.05 SLICE=visit;

RUN;

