8.4 Control of Experiment-wise Type 1 Error

To control the overall experiment-wise type I error at the 0.05 level, a fixed sequence testing approach will be applied. The statistical test will be performed in the following order:

- 1) Change from baseline to Week 7-8 in binge eating days per week between high dose centanafadine and placebo;
- 2) Change from baseline to Week 7-8 in binge eating days per week between low dose centanafadine and placebo;
- 3) Change from baseline to Week 8 in CGI-S score between high dose centanafadine and placebo;

4) Change from baseline to Week 8 in CGI-S score between low dose centanafadine and placebo.

The test for the subsequent hypothesis will be performed only if the test for the previous hypothesis is statistically significant.

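### The covariance fallback for the primary MMRM names a sandwich standard error without a small-sample correction or degrees-of-freedom rule; read as the plain sandwich, it would test at about 6-7.5% with an assumed 10-30 sites

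*SAP*

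**What the plan says.** The primary analysis is an MMRM with an unstructured covariance over six visits and fixed effects for treatment, center, visit and treatment by visit, plus baseline by visit (SAP 8.2.1, Protocol 9.4.1.1). If that fit has a convergence problem, heterogeneous Toeplitz, AR(1) and compound symmetry are tried in order, and the chosen one becomes the primary analysis. Protocol 9.4.1.1 then sets the condition "If a structured covariance has to be used", and SAP 8.2.1 states that the sandwich "estimator of the standard error of the fixed effects parameters will be used in order to deal with possible model misspecification".

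The only small-sample method in the SAP is in the code of 8.2.3.3: "MODEL change=treatment center visit treatment*visit baseline*visit / S CL DDFM=KENWARDROGER". That code is introduced as the analysis with an unstructured matrix.

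Center is a fixed effect after pooling. SAP 8.2.3.2 begins "Small centers will be defined as centers that do not have at least one subject" and completes the rule by requiring an evaluable subject in each arm.

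The primary comparisons are "tested at a significance level of 0.05 (2-sided) in a fixed sequence testing" (SAP 8.2.1). SAP 8.4 adds: "To control the overall experiment-wise type I error at the 0.05 level, a fixed sequence testing approach will be applied". SAP 8.3 applies a similar approach to covariance selection for CGI-S and does not repeat the sandwich sentence.

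**The concern.** The plain sandwich builds its variance from fitted residuals. These are too small on average when the number of subject-level parameters is not small relative to the number of subjects. Here those parameters are three arms, baseline and every analysis center that survives pooling. The standard error is then biased downward, and the bias grows with the number of centers.

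Kenward-Roger does not help. It adjusts the model-based covariance, which the sandwich replaces, and the SAP attaches it only to the unstructured code. The fallback therefore has no stated small-sample protection.

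At stake is the declared 0.05 level of whichever test is read from a fallback model, and the coverage of its confidence interval. If the version is left open, it would be chosen once the data are in hand.

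**Working it through.** **1. The plan's own figures.** SAP Section 4: "Assuming a treatment difference of 1.1 points with a standard deviation of 1.7" and "a sample size of 114 evaluable subjects (38 in each treatment arm) yield at least 80% power".

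- n per arm = 2(1.960 + 0.842)² × 1.7² / 1.1² = 37.5, so 38.
- Power at 38 per arm: 1.1 / (1.7 × √(2/38)) = 2.820, and Φ(2.820 − 1.960) = 80.5%. The two-sample t version gives 79.5%.
- 126 randomized to 114 evaluable implies a loss of 12/126 = 9.5%.

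The sample size is reproduced. The documents state no error rate for the fallback beyond the nominal 0.05.

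**2. Inputs to the simulation.**

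- From the documents: 126 subjects, 1:1:1 allocation within site, six visits, fixed center effects with small centers pooled (a simplified version of SAP 8.2.3.2), baseline by visit, and the Week 8 contrast of each dose with placebo.
- Assumed: number of sites, spread of center sizes, visit correlations, early-visit SDs, baseline mean and SD, and monotone dropout of 10% or 25%.
- Method: 4,000-5,000 null trials per scenario, two contrasts each, Monte Carlo SE about 0.25-0.3 points. The structured covariance was fitted by an approximate EM/moment method, not REML.

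**3. Rejection rate at nominal 5%.** Ranges cover normal, residual-df t and between-subject-df t critical values. CR2 and CR3 are two leverage-corrected sandwiches; CR3 is the stronger correction, of Mancl-DeRouen type.

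| Sites (after pooling) | Structure, dropout | Plain sandwich | CR2-type | CR3-type | Model-based |
|---|---|---|---|---|---|
| No center terms | Toeplitz, 10% | 5.1-5.3 | 4.6-4.9 | 4.3-4.5 | 4.5-4.7 |
| 10 (9.2) | Toeplitz, 10% | 5.9-6.1 | 5.2-5.4 | 4.5-4.7 | 5.0-5.2 |
| 20 (15.9) | Toeplitz, 10% | 6.5-6.8 | 5.2-5.4 | 4.0-4.2 | 5.1-5.3 |
| 20 (15.9) | Toeplitz, 25% | 6.6-6.9 | 5.4-5.7 | 4.1-4.4 | 5.0-5.4 |
| 20 (15.9) | CS, misspecified, 10% | 5.9-6.1 | 5.1-5.2 | 4.0-4.3 | 5.2-5.4 |
| 30 (19.5) | Toeplitz, 10% | 7.1-7.5 | 5.6-5.8 | 4.1-4.3 | 5.6-5.8 |
| 30 (19.5) | AR(1), 25% | 7.2-7.5 | 5.4-5.7 | 3.9-4.2 | 5.0-5.3 |

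**4. Does the bias in the SE explain this?** Take the mean plain SE over the empirical SD of the estimate, r, and compute 2Φ(−1.96 r):

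- 10 sites: r = 0.371/0.389 = 0.954, giving 6.2% (simulated 6.1% with normal critical values).
- 20 sites: r = 0.366/0.386 = 0.948, giving 6.3% (simulated 6.8%).
- 30 sites: r = 0.364/0.391 = 0.931, giving 6.8% (simulated 7.5%).

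The bias accounts for most of the excess. What is left is of the kind that variability of the SE would add.

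**5. A second simulation.** It used separate code, 2,400 replicates, 15% dropout, and 8, 15 and 25 fixed center effects. The plain sandwich rejected 6.4%, 6.8% and 7.8% with normal critical values, and 6.2%, 6.5% and 7.6% with between-subject t (Monte Carlo SE about 0.5 points). Mean SE over empirical SD was 0.382/0.393, 0.379/0.401 and 0.373/0.406, that is 2.8%, 5.5% and 8.1% too small. A fully leverage-corrected sandwich rejected 3.9-5.0%.

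**The case against.** **It is a contingency.** The fallback runs only if the unstructured fit fails. That matrix has 6 × 7 / 2 = 21 parameters for about 126 subjects, and nothing in the documents suggests that failure is likely. If it happened in an assumed 10% of trials, the overall level would be 0.9 × 5 + 0.1 × 6 = 5.1% to 0.9 × 5 + 0.1 × 7.5 = 5.25%. This stands and limits the weight of the point. It does not help the one trial in which the fallback supplies the primary p-value.

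**The plan does not say that the sandwich is uncorrected.** A reader might infer this, since an unqualified sandwich usually means the plain form. The documents leave the version open, so this is a gap in specification and the 6-7.5% is conditional on that reading.

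**The number of sites is unknown, and pooling limits the center terms.** Both are true. Each analysis center needs an evaluable subject in all three arms, so 114 evaluable subjects allow at most 114/3 = 38 center terms, and an assumed 30 sites pooled to about 20. With few centers the problem nearly disappears. Very few sites look less likely, though. Protocol 1.1 gives about 10 months overall and up to 13 weeks per subject, which leaves roughly 7 months to randomize 126, or 18 a month. That is 3.6 a month per site with five sites and 0.9-1.8 with 10-20 sites.

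**The whole testing chain is not inflated.** A reader might infer that all four tests exceed their level together. Binge eating days and CGI-S are separate models, and failure of one fit does not trigger the fallback for the other. For CGI-S the sandwich is only implied, and CGI-S was not simulated. Under the global null, a fixed sequence has the error rate of its first test, so inflation does not accumulate.

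**The strongest correction leans conservative**, at about 4-5%, in a trial with about 80% power. That is why the fix below allows a CR2-type correction as well.

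**Conclusion.** The point holds as a conditional weakness. If the primary unstructured model fails and the plain sandwich is used, the test declared at two-sided 0.05 would run at about 6-7.5% with an assumed 10-30 sites, and at 5.1-5.3% with no center terms. A leverage-corrected sandwich returns it to about 4-6% in the same simulated trials.

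The figures rest on an assumed number of sites, assumed correlations and dropout, and an approximate covariance fit. The two simulations agree that the level rises as center terms are added.

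A level as high as 8% is not supported: the larger simulation reached 7.5% at most, and the 7.8% in the smaller one came with 25 center effects. Nor do the documents support a claim that the planned analysis, unstructured with Kenward-Roger, is anti-conservative. For CGI-S the concern applies only if its own unstructured fit fails and the similar approach in SAP 8.3 is meant to include the sandwich.

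**What to change.** In SAP 8.2.1 and Protocol 9.4.1.1, state that if a structured covariance is used, the standard error will be a small-sample bias-corrected (leverage-adjusted) sandwich, for example CR2-type or Mancl-DeRouen-type, with between-subject degrees of freedom (subjects minus arms minus pooled centers). Choose one version in advance and name a procedure that supports it; the documents name only PROC MIXED. In SAP 8.3, state whether the same rule applies to CGI-S.

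The cost is a few sentences and a small program change. If the fallback is used, confidence intervals become slightly wider. The Mancl-DeRouen type is mildly conservative (about 4-5%); the CR2 type was closer to nominal (4.6-5.8%). If the unstructured model converges, nothing changes.

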8.2.2 Sensitivity Analyses

8.2.2.3 Sensitivity Analyses for Violation of Normality Assumption

MMRM model for the primary efficacy endpoint is a maximum likelihood method that relies on normality assumption. Residual analyses will be carried out to examine model assumption by using Shapiro-Wilk test.

In the case of gross violations of the normality assumptions, nonparametric van Elteren test⁹ will be performed to compare treatment effect in primary efficacy endpoint. The stratification factor is trial center. The van Elteren test is a generalized CMH procedure

useful for stratified continuous data in non-normal setting. It belongs to a general family of Mantel-Haenszel mean score tests. The test is performed via SAS procedure PROC FREQ, by including CMH2 and SCORES=MODRIDIT options in the TABLE statement.

In addition, other methods that are robust to distributional assumption will also be performed to provide different views on the primary efficacy result, these include generalized estimating equations (GEE), weighted GEE (WGEE), and MI-robust regression¹⁰. For MI-van Elteren test and MI-robust regression, imputation datasets will be generated with SAS MI procedure, each dataset will be analyzed, then an overall estimate is derived with SAS MIANALYZE procedure.

